5.3. Exploratory Endpoints

5.3.1. Heterogeneity of treatment effect

We will evaluate heterogeneity of the treatment effect across the following physician characteristics:

- Sex (male vs. female physicians)
- Race/ethnicity (White vs. non-White physicians)
- Attitudes toward video games prior to enrollment (play games versus do not play games)

5.3.2. Mechanisms of action

We will evaluate mediators of the game effect:

- Fidelity of intervention delivery:
 - Dose of intervention (game usage greater than vs. less than 2 hours)
 - Timing between exposure – treatment of patient (first 30 days post-usage vs. days 30-89 versus 90+ days)
- Fidelity of intervention receipt – high versus low perceptual sensitivity; high versus low decisional threshold)

Protocol Deviation (Protocol Deviation 1.5): We changed our classification of "dose" for this analysis from time ≥ 2 hours or < 2 hours to participation in game usage during each intervention period for any amount of time (4 total). We deferred evaluation of mediation by fidelity of intervention receipt because we could not download the needed statistical package to the CMS Virtual Desktop.

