Secondary (outcome analysis) - The proportion of patients over-triaged by physicians in the game-based training group will be equivalent to the proportion over-triaged by physicians in the usual care group

Secondary (mediation) - Under-triage will mediate the effect of the intervention on patient-centered outcomes.

Exploratory (heterogeneity of treatment effect) -

- [1] The intervention will have the same effect on males as on female trial participants.
- [2] The intervention will have the same effect on White compared as on non-White trial participants.
- [3] The intervention will have a greater effect on trial participants who expressed positive attitudes to game-based learning before enrollment compared to those who do not have positive attitudes.
- [4] Trial participants in the game-based training group who use Night Shift 2024 for greater than 2 hours will under-triage a smaller proportion of severely injured patients than those who use the game for less than 2 hours.
- [5] The proportion of patients under-triaged by trial participants will be lower immediately after exposure to the intervention (i.e., in the first 30 days) compared to late post-exposure period (i.e., 30-89 days).
- [6] Trial participants with greater parameters of compliance on SONAR (the experimental tool to measure determinants of physicians' decision making) will under-triage a smaller proportion of severely injured patients than those with lower parameters of compliance.

**2. \* Describe the relevant prior experience and gaps in current knowledge including preliminary data. Provide for the scientific or scholarly background for, rationale for, and significance of the research based on existing literature and how it will add to existing knowledge:**

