## Research Activities

- 1. \* Provide a detailed description of all research activities (including screening and follow-up procedures) that will be performed for the purpose of this research study. This description of activities should be complete and of sufficient detail to permit an assessment of associated risks.**

Intervention and Control:

We have partnered with 3 national physician staffing groups. Cumulatively, these groups employ approximately 4500 physicians, cover  $\geq 30$  states, staff  $\geq 600$  emergency departments (EDs), and provide care to  $\geq 16$  million patients each year. We will ask physician leaders of the organizations, with which we have partnered, to distribute an email to their staff that describes the trial, and includes a link to the consent form. Physicians who provide consent will then receive a survey that collects demographic data which will allow us to assess eligibility.

Qualified physicians will be randomized with an allocation ratio of 1:1, based on a randomization schema generated by our statistician ([name]) in STATA 17.0 (Statacorp, TX) with blocks of 4 or 8.6. Trial coordinators will link the randomization schema to the enrollment data, and will assign participants to groups. Although we cannot maintain blinding after allocation, our data analysts will not have access to that information.

We will pre-load new iPads with Night Shift 2024 and will mail the devices to those allocated to the intervention group. We will ask participants to spend a minimum of two hours playing Night Shift 2024 within 2 weeks of receiving their device, and then return to the game for 20 minutes at 3, 6, and 9 months. Participants will keep their iPad as a fixed honorarium (approximate value: \$350), and will also receive a conditional monetary honorarium if they complete any of the booster doses that they complete (\$25/session). We will issue three email reminders and a phone call during the first two weeks after enrollment, and then quarterly reminders during the subsequent trial period. Participants have the option of not completing the assigned study task, but we do not have pre-specified criteria for discontinuing or modifying the allocated intervention.

Participants in the usual care group will complete outcome assessment tools, and will receive a conditional, wage-based honorarium (\$100/hour spent) upon completion of study tasks.

Interviews:

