4.1.1. Dosing and administration

Participants are asked to complete a minimum of 2 hours of gameplay within 2 weeks of receiving their device, followed by three 20-minute booster sessions at approximately 4, 7, and 10 months post-enrollment. Participants receive three email reminders and a phone call during the first two weeks, followed by quarterly reminders thereafter. A conditional honorarium of \$20 per completed booster session is provided. Participants also keep the trial iPad at the end of the year, as part of their honorarium.

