7.7.3. Mediation of the game's effect on under-triage

We test 4 mediators of the treatment effect: intervention dose (≥ 2 hours versus < 2 hours), timing of game use–treatment of patient (≤ 30 days versus 39-90 days versus > 90 days versus none), and fidelity of intervention receipt (perceptual sensitivity and decisional threshold). To evaluate exposure–effect relationships, we model the probability of under-triage and included an interaction term between the mediator and patient injury severity. To evaluate fidelity of intervention receipt relationships, we conduct a causal mediation analysis to assess whether the effect of the intervention on under-triage is mediated through perceptual sensitivity (i.e., diagnostic ability – targeted by the game) or by decisional threshold (i.e., willingness to transfer). The total effect of the intervention is decomposed into natural direct and natural indirect effects representing pathways independent of and operating through the mediator.

Protocol Deviation (Version 1.5): We deferred the mediation analysis testing the influence of fidelity of intervention receipt because we could not obtain the correct statistical package to run the analysis on the CMS Virtual Desktop. We also reconceptualized dose as the number of intervention periods during which game play occurred for any amount of time (out of 4 total). Dose therefore represented actual treatment and not assignment.

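### The timing analysis counts from actual, optional game use, so its 90+ day group is probably dominated by physicians who skipped boosters and cannot show wear-off of training

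*SAP*

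**What the plan says.** SAP 5.3.2 lists timing as a mechanism of action, in three windows: "first 30 days post-usage vs. days 30-89 versus 90+ days". SAP 7.7.3, which specifies the analysis, uses other categories: up to 30 days "versus 39-90 days versus > 90 days versus none". Days 31 to 38 then fall in no category, and it is not stated who belongs to the last one. Exploratory hypothesis [5] in the Protocol (Study Aims) has only two windows; it expects under-triage to be "lower immediately after exposure to the intervention (i.e., in the first 30 days) compared to late post-exposure period (i.e., 30-89 days".

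Use is logged by the app (SAP 4.1.2). The first dose is a "minimum of 2 hours of gameplay within 2 weeks of receiving their device" (SAP 4.1.1). The SAP then schedules "three 20-minute booster sessions at approximately 4, 7, and 10 months post-enrollment", while the Protocol (Research Activities) asks physicians to "return to the game for 20 minutes at 3, 6, and 9 months". The Protocol's section on ongoing consent leaves each booster to the physician's choice.

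For dose and timing, SAP 7.7.3 models the probability of under-triage with an interaction between the mediator and injury severity. It states no term for sessions played or for time since enrollment. From version 1.4 the primary model (SAP 7.5) has no baseline covariates and clusters by physician only. SAP 7.7 labels the exploratory analyses hypothesis-generating.

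**The concern.** Time since play is something the physician chooses after randomization. Boosters come about every three months, so a physician reaches 90 days without play mainly by missing one. The early and the 90+ day groups would then contain different kinds of physician, and a difference between them mixes wear-off with whatever separates those who keep playing from those who stop.

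The model cannot separate the two. SAP 7.2 expects a median of 1-2 eligible patients per physician, so the contrast is mainly between physicians, and a random intercept does not remove that confounding. Usual-education physicians have no usage date. Even if they form the unexplained fourth category, they are not split by window and cannot show what time alone does.

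At stake is the reading of a result that the SAP appendix lists as reported in the manuscript. Higher under-triage at 90+ days could be taken as decay, and so as an argument for boosters, when training had not worn off at all. SAP 7.7.3 says of the redefined dose that it reflects treatment taken rather than assigned; it gives no such caution for timing.

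**Working it through.** The plan gives no figure to reproduce. The check asks who fills each window if timing runs from the most recent session.

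**Inputs.** Follow-up is 365 days from enrollment (SAP 3.2.2, deviation note). Boosters fall at months 3, 6 and 9 (days 91, 183, 274) or at months 4, 7 and 10 (days 122, 213, 304). Assumptions: first play on day 14, and patients arriving evenly over time.

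**Day count.** For each day d from 0 to 364, the gap is d minus the latest play day not after d. Days 0-13 precede any play.

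| Physician | up to 30 d | 31-90 d | over 90 d |
|---|---|---|---|
| Full adherer, 3/6/9 | 124 | 226 | 1 |
| Full adherer, 4/7/10 | 124 | 210 | 17 |
| Played once | 31 | 60 | 260 |

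Each row adds to 351, which is 365 - 14. With the boundary at 90 days or more (SAP 5.3.2), the last column becomes 4, 20 and 261.

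**Simple mixture.** If half of players are full adherers and half play once, once-only players supply:
- up to 30 days: 31/(31 + 124) = 20%
- 31-90 days: 60/(60 + 226) = 21% or 60/(60 + 210) = 22%
- over 90 days: 260/(260 + 1) = 99.6% or 260/(260 + 17) = 94%

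The sorting is almost entirely in the last group. Once-only players hold half of the 90+ day time when their share of players is 4/(4 + 261) = 1.5% on the 3/6/9 schedule, or 20/(20 + 261) = 7% on 4/7/10.

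**Range of skipping.** The documents give no adherence rate, so it was varied. Each scenario had 4,000 simulated physicians, first play on days 0-28, boosters played on time or up to 14 or 30 days late, and each booster skipped independently with probability q. The share of physicians who skip at least one booster is 1 - (1 - q)^3, or 14% at q = 0.05 and 27% at q = 0.10. Their share of 90+ day time, over both schedules and all delays, was 32-81% at q = 0.05 and 51-90% at q = 0.10.

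On the SAP schedule with boosters up to 14 days late:

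| q | under 30 d | 30-89 d | 90+ d |
|---|---|---|---|
| 0.20 | 38% | 39% | 78% |
| 0.50 | 80% | 81% | 97% |

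**False decay when there is none.** Suppose, as an assumption, that under-triage never changes with time, is 70% in full adherers, and rises evenly to 80% in those who skip every booster. In the same scenario, 90+ against under 30 days shows 73.5% against 71.5% at q = 0.20 (2.0 points) and 76.4% against 74.0% at q = 0.50 (2.4 points). Under 30 against 30-89 days shows 0.0 to 0.1 points.

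**The case against.** The strongest reply is that hypothesis [5] contains no 90+ day group. Its late period is days 30-89, which adherent physicians fill after every session, and the counts above show almost no sorting there. This stands. A reader might infer that hypothesis [5] cannot be tested because its late group is mostly booster-skippers; the Protocol's definition does not support that. The problem lies in the group that the SAP adds. Even so, both contrasts rest on chosen play dates, so neither is randomized.

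Second, neither SAP section says that timing runs from the most recent session. If it ran from the first, boosters would not restart the clock and the counts would not apply. This also stands; the reference session has to be stated.

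Third, that skippers form most of the 90+ day group is an inference. With 5% skipping per booster they may hold only about a third of it.

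Fourth, a reader might infer that the windows fall in fixed parts of the year because the Protocol plans 3-4 weeks of enrollment. The SAP's revision history records slow and delayed enrollment, so this is not supported. Study time does differ between groups when skipping is common: at q = 0.50 the mean study day is 222-235 at 90+ days against 129-157 under 30 days. At q = 0.05-0.10 on the SAP schedule the gap is small or reversed (168-189 against 174-187).

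Last, the analysis is exploratory and no passage says that it will be used to support boosters. That limits the consequence, but a hypothesis-generating label does not tell the reader that the groups are self-selected.

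**Conclusion.** The point holds for the 90+ day group. Timing from actual use is a post-randomization exposure, and no adjustment for adherence or time since enrollment is stated. If the clock runs from the most recent session, a full adherer spends about 1-20 of 365 days in that group against about 260 for a physician who played once. The group is then probably dominated by skippers: a majority at 10% or more skipping per booster, 32-81% at 5%. A difference at 90+ days cannot be read as wear-off; under the illustrative 10-point gradient, 2.0-2.4 points would appear with none.

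These figures rest on even patient flow, the assumed play dates and assumed skip rates. The contrast of hypothesis [5] is little affected by skipping but remains non-randomized. The primary test is untouched. This is a worthwhile, cheap improvement to an exploratory analysis.

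**What to change.** - State which session starts the clock and who is in the fourth category of SAP 7.7.3.
- Reconcile the windows in Protocol hypothesis [5], SAP 5.3.2 and SAP 7.7.3, and the booster months in the Protocol (Research Activities) and SAP 4.1.1.
- In both arms, classify each patient by days since the most recent scheduled session, counted from the physician's enrollment. Fit arm, window and arm-by-window in the primary model, and base hypothesis [5] (first 30 against 30-89 days) on the arm difference in each window. Label this post hoc, because the data are locked.
- Keep the actual-use analysis as descriptive, label it non-randomized, and draw no decay conclusion from its 90+ day group.

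The cost is SAP wording, one derived variable and one model. Enrollment dates are already needed for the 365-day follow-up. The first session is due relative to device receipt in SAP 4.1.1 but to enrollment in the Protocol's Study Aims. Controls receive no device, so one rule counted from enrollment must serve both arms.

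The comparison has limits. It is diluted by non-adherence, imprecise with 1-2 patients per physician, and estimates the effect by assigned rather than actual time since play. Scheduled sessions leave few days beyond 90, so the design holds little randomized information about that period.

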5.4. Implementation Endpoints

Barriers and facilitators of adoption, implementation, and maintenance of guideline-concordant trauma triage are assessed through semi-structured interviews with a subset of intervention-arm physicians (n = 20) and key decision makers (n = 80-100). These endpoints are analyzed using qualitative methods and are reported separately from the quantitative effectiveness analyses.

6. TRIAL CONDUCT

6.1. Randomization

Physicians are randomized 1:1 to the intervention or control arm using a permuted block design with variable block sizes of 4 or 6, generated by the study statistician in Stata 17.0 (StataCorp, Texas). Trial coordinators link the randomization schema to enrollment data and assign participants to groups. To address equity, minority physicians (female, non-White) are oversampled and may comprise up to 50% of the final cohort.

The use of variable block sizes of 4 or 6 is disclosed in this public protocol, which creates a theoretical risk that future allocation sequences could be predicted by individuals with access to sequential enrollment data. This risk is mitigated by the following four features of the trial design:

- enrollment is conducted entirely remotely and centrally via an online platform, with no face-to-face interaction between recruiting staff and participants
- allocation assignments are masked to all trial staff until after the completion of data cleaning
- use of variable rather than fixed block sizes reduces predictability even when the range of block sizes is publicly known
- primary outcome is assessed using Medicare Fee-for-Service claims, an administrative data source entirely independent of the enrollment and allocation process.

Protocol Deviation (Protocol Deviation 1.1): We included all eligible respondents without attempting to oversample minority physicians because of difficulty finding willing participants.

6.2. Blinding

Full blinding is not possible in this trial given the nature of the intervention. Participants are aware of their assigned arm following allocation. However, data analysts are kept masked to treatment assignment throughout the analysis period to minimize the risk of bias in outcome assessment.

6.3. Data Collection

Four types of source data are collected:

- **Physician self-reported data:** Baseline demographic and professional characteristics are collected via an online Qualtrics survey at enrollment. Game usage statistics are collected from the *Night Shift 2024* application. Responses to the User Engagement Scale Short Form are collected from a trial portal.
- **Physician experimental data:** Physicians completed a virtual simulation (SONAR) in which they responded to 36 cases (26 with injury), allowing us to calculate signal

detection theory metrics: perceptual sensitivity and decisional threshold. These metrics allow understanding of fidelity of intervention receipt.

- **Medicare claims data:** Inpatient, Outpatient, Skilled Nursing Facility, and Professional Claims filed with Medicare Fee-for-Service and Advantage for beneficiaries aged 65 or older with ICD-10 codes associated with injuries are obtained from CMS for the trial period (2024), with flanking quarters (Q4 2023 and Q1 2025) to capture preceding and follow-up care. Claims are used to ascertain patient eligibility, injury severity, triage decisions, and patient outcomes.
- **Qualitative data:** Audio recordings and transcripts of semi-structured interviews with trial physician participants and key decision makers are collected via Pitt Zoom.

All primary quantitative and qualitative trial data are stored on the University of Pittsburgh Sharepoint. All CMS data are stored on the Virtual Desktop. Participants are assigned unique study identifiers at enrollment; identifying information is stored separately from research data.

Protocol Deviation (Protocol Deviation 1.3): As noted above, we did not obtain Medicare Advantage claims, nor did we obtain Medicare Skilled Nursing Facility claims.

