4.1.3. Measurement of fidelity of treatment receipt

We define intervention receipt as evidence that participants understand and can use the skills or knowledge learned during the intervention, and will evaluate it in three ways. First, we will ask participants (intervention and control) to describe their understanding of the central principle of trauma triage on the first post-enrollment survey. Second, we will ask them to complete an online tool that assesses physician behavior in trauma triage (SONAR). SONAR is a 2D web-based serious game, during which physicians must triage 30 trauma patients (15 with severe injuries; 15 with minor injuries). The game evaluates decisions using the guidelines published by the American College of Surgeons – Committee on Trauma, and produces two sets of metrics: compliance with guidelines (e.g., under-triage) and signal detection parameters. Signal detection theory came to prominence during World War II and allows inferences about the sources of non-compliance with clinical practice guidelines by parsing the influence of perceptual sensitivity (the ability to distinguish between minimally and severely injured patients) and decisional thresholds (preferences to err on the side of under- or over-triage) on decisions.

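### SAP 4.1.3 and 6.3 give SONAR two case sets that cannot both be right, and 5.3.2 cuts its scores into high and low; settle both before the deferred receipt mediation is run.

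*SAP*

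**What the plan says.** SAP 4.1.3 describes SONAR as a web-based game in which "physicians must triage 30 trauma patients (15 with severe injuries; 15 with minor injuries". It defines "perceptual sensitivity (the ability to distinguish between minimally and severely injured patients" and treats the decisional threshold as a preference for erring towards under- or over-triage. It lists guideline-compliance metrics as a separate set of outputs.

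SAP 6.3 describes the same named tool as a simulation "in which they responded to 36 cases (26 with injury", from which the team obtains the signal "detection theory metrics: perceptual sensitivity and decisional threshold". It does not divide the 26 into severe and minor, and it does not say what happens to the other cases.

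SAP 5.3.2 lists the receipt mediators as "high versus low perceptual sensitivity; high versus low decisional threshold", with no cut-point. SAP 7.7.3 names "fidelity of intervention receipt (perceptual sensitivity and decisional threshold" among its four mediators and plans a causal mediation analysis with natural direct and indirect effects. It dichotomises dose but gives no cut for the two SONAR scores. A version 1.5 note there says: "We deferred the mediation analysis testing the influence of fidelity of intervention receipt". The stated reason is that the statistical package was unavailable.

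In the Protocol (Study Aims), exploratory hypothesis [6] concerns "Trial participants with greater parameters of compliance on SONAR".

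**The concern.** Both signal-detection scores come from a hit rate and a false-alarm rate. Under the definition in 4.1.3, the hit rate is taken over the severe cases shown and the false-alarm rate over the minor-injury cases shown. A plan that gives two case sets for one tool leaves those denominators undefined. A plan that mentions non-injured cases without saying whether they are scored leaves the noise class undefined too.

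The receipt mediation is meant to separate diagnostic ability from willingness to transfer. The choice of scored cases can move both scores, so that separation depends on it. The high/low wording in 5.3.2 adds a second weakness: it coarsens scores that already rest on few cases per class. An analyst picking up the deferred work could not reproduce the mediators from this SAP.

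**Working it through.** **1. Do the counts reconcile?**
- SAP 4.1.3: 15 + 15 = 30, all injured. This is internally consistent.
- SAP 6.3: 36 − 26 = 10 cases without injury.
- Filler cases do not bridge the gap: 30 + 6 = 36 matches the total but leaves 30 injured, and 30 − 26 = 4. From 4.1.3 to 6.3 the total rises by 6 while the injured count falls by 4.
- Neither section mentions practice cases, unscored cases or a second version. The revision history and the appendix table record no change to SONAR. The only deviation note in 6.3 concerns claims data.

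**2. How far do the scores depend on the case set?** Equal-variance signal detection, with a log-linear correction: H = (hits + 0.5)/(n_severe + 1), F = (false alarms + 0.5)/(n_noise + 1), d′ = z(H) − z(F), c = −½[z(H) + z(F)]. Assume one physician with 9 hits and 4 false alarms. The documents give no split of the 26, so every split below except 15/15 is an assumption.

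| Severe / noise cases | d′ | c |
|---|---|---|
| 15 / 15 (SAP 4.1.3) | 0.82 | 0.17 |
| 13 / 13 (26 injured, even split) | 0.93 | 0.00 |
| 10 / 16 | 1.73 | −0.23 |
| 16 / 10 | 0.38 | 0.04 |
| 13 / 23 (10 non-injured counted as noise) | 1.35 | 0.21 |

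For example, at 15/15, H = 9.5/16 = 0.594 and F = 4.5/16 = 0.281, so d′ = 0.237 + 0.579 = 0.82. The table shows how sensitive the scores are to the denominators. It does not estimate an error that occurred.

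**3. How precise is one physician's d′?** Var(d′) = H(1−H)/(n_severe·φ(z_H)²) + F(1−F)/(n_noise·φ(z_F)²). With H = 0.60 and F = 0.25 (assumed), the SE is 0.48 for 15/15 and 0.52 for 13/13. If true d′ has an SD of 0.4 to 0.8 between physicians (assumed), reliability runs from 0.16/(0.16 + 0.52²) = 0.37 to 0.64/(0.64 + 0.48²) = 0.74.

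**4. What does a high/low cut lose?** For a normal score cut at its median, the correlation between the score and the indicator is φ(0)/0.5 = 0.399/0.5 = 0.798. Its square is 2/π = 0.64, so about 36% of the information is discarded. The SAP states no cut-point; a median split is the assumption here.

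**The case against.** The best reply is that this is a slip of description in an analysis that has not been run. Much of that stands. The primary, secondary and safety endpoints come from claims and do not use SONAR. The revision history removes the receipt analysis, 5.3.2 and 7.7.3 call it deferred, and the appendix lists it as not performed.

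It is also fair that the tool itself produces the metrics, so nothing suggests anyone took denominators from the SAP text. The definition in 4.1.3 already points to minor injuries as the noise class, which argues against the 13/23 row. The two sections differ in tense: 4.1.3 is a plan and 6.3 a report. Planned versus delivered content is therefore one possible explanation, though the documents do not settle it. The high/low wording appears only in the endpoint list, not in the operative section, 7.7.3.

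Three stronger readings are tempting and not supported.
- A reader might infer that two instruments were used or that scores are wrong. Both sections name one tool, and no mis-scored physician is shown.
- A reader might infer that the whole mechanism objective rests on SONAR. Dose and timing of exposure are also mechanism analyses; they were kept and do not use it.
- A reader might carry the d′ and c figures over to Protocol hypothesis [6]. That hypothesis is worded in terms of compliance parameters, which 4.1.3 lists apart from the signal-detection ones.

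The reply does not remove the contradiction. Both statements are current text, and a deferred analysis can still be run.

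**Conclusion.** The inconsistency is certain: 30 injured cases and 26 injured cases cannot describe one set, and nothing in the documents explains the change. Which count is right cannot be told from them. The consequence is limited to the exploratory mediation by perceptual sensitivity and decisional threshold, and it is conditional on how that analysis is eventually scored. For the assumed responses, d′ runs from 0.38 to 1.73 across the severe/minor splits tried, a wide range for a single physician. It rests on holding 9 hits and 4 false alarms fixed while the denominators change.

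The high/low cut is a separate, avoidable loss of about 36% under a median split of a normal score. It should not be read as simply pulling every association towards zero. In the planned mediation analysis, error in the mediator would typically shrink the indirect effect and move the remainder into the direct effect. That error stays whether the score is cut or continuous.

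**What to change.** Before the deferred analysis is run:

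1. Reconcile SAP 4.1.3 and 6.3 to the case set actually delivered, giving the severe, minor and non-injured counts and stating which cases are scored.
2. Confirm that hits were scored on severe cases and false alarms on minor-injury cases, in line with the definition in 4.1.3. Re-score only if they were not.
3. If two versions of the tool were used, say so and score each on its own counts.
4. In 5.3.2, replace the high/low categories with continuous sensitivity and threshold scores, and state the same scale in 7.7.3.
5. Note with the results that measurement error in the scores remains and which way it is likely to move the direct and indirect effects.

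The cost is a few sentences of SAP text and a check of the scoring rule. Re-scoring, if needed, uses data already held. The small downside is that effects are reported per SD instead of as a high-versus-low contrast.
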